#### Assessing SARS-CoV-2 infection Via Serologic Testing

In both the market+ and individual-level experiment, we are interested in assessing the impacts of mask use on COVID-19 infections separately from respiratory disease. To do so, we will use serological testing.

In the market+ experiment, serological tests will be conducted 12 weeks after baseline for individuals who reported respiratory disease symptoms during our intervention. We will follow-up with these individuals using household interviews and conduct serology tests using blood spots obtained from finger pricks. The number of positive serology tests in this population will tell us rates of “symptomatic COVID-19”. We will then compare rates of symptomatic COVID-19 between the treatment and control group. For example, if 5% of the 350,000 respondents in the market+ experiment report respiratory symptoms, we will conduct 17,500 such tests. Symptomatic COVID-19 will be a subset of cases of respiratory disease. Power will be similar to our respiratory disease calculation above, especially if most respiratory disease cases are COVID-19. If infection rates are higher than expected, we will cap the number of serology tests at 20,000, which should be sufficient to have ample power based on the calculation above. In addition, we will conduct baseline and endline serologic testing in a random selection of 5,000 households. This is to evaluate factors that could be related to differential reporting between the control and treatment groups.

Dried blood spot samples will be collected at endline from individuals who reported COVID-like symptoms as well as from the 5,000 randomly-selected individuals at baseline and endline. Rapid diagnostic tests will also be performed at endline. Only samples that are positive by rapid diagnostic test and 5% of negative samples will undergo further evaluation by ELISA.

In the individual experiment, we will conduct both baseline serology tests and serology tests after 12 weeks. In both cases, these will use blood spots obtained via finger pricks administered by health workers. We will start by testing endline blood spots and only perform baseline testing on those individuals who test positive at endline by rapid diagnostic testing, plus 5% of negative tests. This will be slightly under 20,000 tests, depending on rates of serologic positivity. The baseline test in the individual experiment will increase power by allowing us to control for COVID-19 infections that occurred pre-intervention.

The blood drops will be collected by pricking a participant’s finger using a sterile, single-use lancet (very small device with a sharp point). The first drop of blood will be wiped away (not used). The next 3 or 5 drops will be put on the collection card, and will be used for the tests. Occasionally it is necessary to stick the finger a second time in order to get enough blood.

The blood will be tested for antibodies against coronavirus. We will be collecting blood samples at the beginning and end of the study for the individual-level experiment and at the end of the study for the market-level experiment. The results from the rapid test will be known at the time of collection, but these

results must be confirmed with a second test. Results of the confirmatory test will not be returned to participants.

More information on procedures to safely collect the blood samples are outlined in the attachment "SOP for collection of dried blood spots."

Additional serologic infectious disease testing will also be performed to evaluate burden of other diseases in the population. Using the residual sera after performing testing for SARS-CoV-2 antibodies, other serologic infectious disease testing will be performed to evaluate disease burden across the sampled populations. The final list of diseases is yet to be determined but may include dengue, chikungunya, malaria, typhoid, etc. These tests will be conducted using single-plex or multi-plex platforms for IgG detection, depending on test availability.

All testing will be carried out at North South University in Dhaka. Samples will be delivered to the lab weekly where they will be stored until testing. Dried blood spots will be stored in a freezer at North South University (Dhaka, Bangladesh) and stored for future use. Future testing could include additional antibody or PCR testing for SARS-CoV-2 or other infectious diseases. No genetic testing will be performed on these samples. If seropositivity rates are low, samples may undergo pooled testing in batches of 5-10 to reduce the total number of tests required. All samples will be run using a quantitative ELISA assay to evaluate presence of IgM and IgG. Untested samples from the market+ experiment will be stored for possible future testing to evaluate asymptomatic infections.

The ELISA serology test is for research purposes only. It will not guide clinical decision making, and results will not be provided to study participants. We are currently planning to use the InBios IgG ELISA, a commercially available test. The subject and biospecimen data collected will not be submitted to or held by the FDA, nor will it be used to determine the safety or efficacy of the test.

#### 4. Genetic Testing N/A

##### A. Describe

- i. the types of future research to be conducted using the materials, specifying if immortalization of cell lines, whole exome or genome sequencing, genome wide association studies, or animal studies are planned *Write here*
- ii. the plan for the collection of material or the conditions under which material will be received *Write here*
- iii. the types of information about the donor/individual contributors that will be entered into a database *Write here*
- iv. the methods to uphold confidentiality *Write here*

- B. What are the conditions or procedures for sharing of materials and/or distributing for future research projects? *Write here*
- C. Is widespread sharing of materials planned? *Write here*
- D. When and under what conditions will materials be stripped of all identifiers? *Write here*
- E. Can donor-subjects withdraw their materials at any time, and/or withdraw the identifiers that connect them to their materials? *Write here*

---

 <https://inbios.com/scov-2-detect-igg-elisa-kit-2/>

- i. How will requests to withdraw materials be handled (e.g., material no longer identified: that is, anonymized) or material destroyed? *Write here*
- F. Describe the provisions for protection of participant privacy *Write here*
- G. Describe the methods for the security of storage and sharing of materials *Write here*

5. **Participant Population:** Provide a detailed description of the types of participants who will be recruited into this study.

Participants for the market+ study will consist of individuals residing in each of the villages selected for the study. For the individual-level study, participants will consist of vendors at selected indoor markets.

6. **Describe** how access to the population will be gained in the study.

Our local implementing partners IPA Bangladesh will gain permission and support from all relevant local authorities and community leaders to access the research sites and populations targeted in this study. In particular, they will coordinate with Imams and mosque officials, market managers and authorities, tea stall vendors, indoor market vendors, and village and community leaders in each of the participating research sites.

7. **Participant classification:** Check off all classifications of participants that will be specifically recruited for enrollment in the research project. Will participants who may require additional safeguards or other considerations be enrolled in the study? If so, identify the population of participants requiring special safeguards and provide a justification for their involvement.

 Children	 Healthy	 Fetal material, placenta, or dead fetus
 Non-English Speaking	 Prisoners	 Economically disadvantaged persons
 Decisionally Impaired	 Employees	 Pregnant women and/or fetuses
 Yale Students	 Females of childbearing potential	

Click or tap here to enter text.

NOTE: Is this research proposal designed to enroll children who are wards of the state as potential participants?  Yes  No

8. **Inclusion/Exclusion Criteria:** What are the criteria used to determine participant inclusion or exclusion?

We have collected data on respiratory symptoms throughout Bangladesh using phone surveys since April 2020. These studies were covered by a previous IPA IRB. We are using these data to identify 700 markets+ throughout Bangladesh with high baseline rates of respiratory disease symptoms. Half of the 700 markets+ will be randomly assigned to the treatment and control groups. We expect to successfully survey directly 500 people per mouza per wave across 700 mouzas, or 350,000 people for each of the 3 waves of the survey.

We will also identify around 10,000 indoor market vendors throughout Bangladesh, and randomly assign half of these vendors to each of the treatment and controls arms of the intervention.

#### SECTION V: RECRUITMENT/CONSENT AND ASSENT PROCEDURES

**1. Recruitment Procedures:**

a. Describe how potential participants will be identified and contacted, and by whom.

- At participating mosques, worshippers will be given masks as they enter mosques for Friday Jumuah prayer in the treatment arm, as well as brochures with public health guidelines and recommendations as they exit the mosques. This will be conducted by members of the IPA Bangladesh team. Imams or mosque officials will also communicate with their community members to encourage compliance with the study's public health guidelines.
- At participating markets, we will reach vendors and market-goers as they enter each market in the treatment arm and receive masks handed out by members of the IPA Bangladesh team. We will also hire monitors who will go around each market throughout the study period to encourage people to wear masks.
- In public areas including tea stalls and factories, we will provide individuals with masks handed out by members of the IPA Bangladesh team.
- At participating indoor markets, we will reach vendors at their stalls and provide them with masks handed out by members of the IPA Bangladesh team.
- At participating villages, we will conduct visits inside communities to hand out masks to individual community members.

Are you collecting any information about the individuals prior to their signing a consent form?

Yes  No

If yes, indicate what information you will be collecting and how it will be gathered (*phone screen, paper questionnaire, etc.*) [Click or tap here to enter text.](#)

**2. Indicate recruitment methods below.** Attach copies of any recruitment materials that will be used.

 Flyers	 Internet/web postings	 Radio
 Posters	 Mass email solicitation	 Telephone
 Letter	 Departmental/Center website	 Television
 Through local NGO or other local contact	 Departmental/Center research boards	 Newspaper
 Table set-up / in-person recruitment of public	 Snowball sampling	
 Classroom recruitment	 Social Media (Twitter/Facebook):	
 Other:		

**3. Targeted Enrollment: Give the number of participants:**

a. Targeted for enrollment at Yale for this protocol

Not Applicable

b. If this is a multi-site study, give the total number of participants targeted across all sites

In the market+ intervention, we expect to successfully survey directly 500 people per market+ per wave across 700 markets+, or 350,000 people for each of the 3 waves of the survey. In the individual intervention, we expect to reach 10,000 indoor market vendors.

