#### Village-level experiment (Research Questions 1, 2 and 3)

#### *Study Design*

We will start by identifying 700 markets, along with the most centrally located village and the mosque attended by most residents of that village. We expect this to comprise about 250 households, or 500 adults per village. We will call this entity a “market+” (plural: markets+).

In order to evaluate whether masks prevent the spread of COVID by preventing transmission and/or protecting the wearer, we will randomize markets+ into treatment and control groups. Our intervention will involve distributing masks at no cost at mosques, markets and directly at people’s homes. We will combine the mask distribution with appropriate behavior change communication and messaging involving imams, market committee leadership and community leaders. We will stratify on markets+ within the same upazila, keeping all markets+ at least 5-10 km apart to minimize spillovers.

Half of the 700 markets+ will be assigned to the treatment group. We intend to stratify to that treatment and control groups are as balanced as possible in terms of ex ante likelihood of COVID-19 infections. To do so, we will: 1) stratify by upazilas and 2) stratify by unions that have similar case rates. For “markets+” that are in the same Upazila and in unions with similar rates of cases, we will list them in order of population and do pairwise stratification by population.

[figure not shown]

Figure 1: Village-level experiment study design

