#### Secondary outcomes:

1. The impact of the intervention on mask use in mosques, markets and other public areas, including the fraction a) appropriately (covering the nose and chin) wearing a mask distributed by our project, b) appropriately wearing a mask that was not distributed by our project, c) inappropriately wearing any a mask or other face covering, or d) are not wearing a face covering at all, and also the fraction specifically wearing our distinctive mask.
2. Prevalence of symptoms of respiratory infection among all individuals for whom we collect phone numbers
3. The prevalence of symptoms of respiratory infection, disaggregated by market vendors, market-goers, imams, mosque-workers, and mosque-goers and none of the above.
4. Number and fraction of pharmacy customers that purchase medicines for symptoms of respiratory infections.
5. Physical distancing behavior measured by direct observation of behavior in mosques.
6. Percentage of adults out of their homes and visiting tea stalls and mosques.
7. Any available data (likely incomplete) on hospitalizations and COVID-19 mortality in each community. This data will be aggregate data which is de-identified from local hospitals and clinics. We expect this data to be sparse and incomplete.
8. Effectiveness of pre-intervention masks by examining the effect size of the intervention with respect to the percent of mask-wearing prior to the intervention. For example, the intervention may increase mask use to 30% in both different treatment villages. If the effect of the intervention on COVID-19 infection rate is the same in villages where people 0% of people were wearing face coverings pre-intervention and where 50% of people were wearing face coverings pre-intervention, this would suggest that the type of face coverings worn prior to the intervention were ineffective.

This analysis uses the variation generated by the randomization but also requires additional assumptions since the baseline rate of mask use is not randomized.

*Intervention activities*

In the treatment arm we will conduct the following intervention activities for four weeks:

- Role modeling
  - Ask imams, public officials and community leaders to commit to wearing masks whenever they leave the house, including while imams deliver prayer at the mosque. It's important to get all influential role-models engaged with our intervention.
- Communities and households:

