#### Symptoms of respiratory symptoms

- Go to each household and conduct in-person our baseline survey (same questions as telephone survey). We will elicit consent, as well as collecting demographic information such as age, gender, employment status, and household size information.
- Conduct two waves of follow-up phone surveys to elicit respiratory symptoms and ask about mask use: we will conduct these five weeks after the start of the intervention, and nine weeks after the start, with the potential for longer-term follow-up surveys. We will determine the response rate in the pilot, but our initial estimate is at least 70%.
- Monitor differences in response rates between the treatment and control group to assess whether there is possible response bias from people in the treatment group being more likely to complete our full telephone survey (we suggest other ways of mitigating this potential bias below). For 5,000 randomly chosen households, we will draw blood spots from one adult identified as the highest-risk in their household in terms of number of contacts (2,500 in the control group and 2,500 in the treatment group); the blood spots will be collected in the baseline household survey and used for serology tests. This will allow us to see if survey response rates to our telephone survey correlate differently with baseline infectivity in the treatment and control group.
- Recruit and train local pharmacists to collect data on the number, fraction, and gender of customers that report various symptoms of respiratory infection. Pharmacists will also record the count and purpose of the medicines purchase to treat fever, dry cough or sore throat, and the number of family members with each symptom.

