#### Serology tests

- Among adults who report respiratory symptoms in any of our telephone surveys, we will draw blood spots 12 weeks after the initial intervention and conduct serological testing to identify “symptomatic infected”. If the number of symptomatic individuals exceeds 20,000, we will randomly choose 20,000 to be tested in this way from all symptomatic individuals.
- Collect bloodspots for serological testing in 5,000 randomly chosen baseline households. At endline (12 weeks after the intervention begins) we will again collect bloodspots for serological testing in these same 5,000 households.

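### The target of 350,000 people surveyed in each of three waves needs about 100% response, but the protocol expects at least 70% by phone in the two follow-up waves

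*Protocol*

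**What the plan says.** The frame comes from the Study Design of the village-level experiment. There are 700 markets+, and of each the protocol says "We expect this to comprise about 250 households, or 500 adults per village".

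The enrolment figure is in Section V.3: "we expect to successfully survey directly 500 people per market+ per wave across 700 markets+, or 350,000 people for each of the 3 waves". Section IV.8 repeats it per mouza, with the same 700 and 500. Section V.4 attributes the estimates to power calculations.

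Under Data collection, the respiratory-symptoms item describes an in-person baseline survey at each household and then the follow-up: "Conduct two waves of follow-up phone surveys to elicit respiratory symptoms and ask about mask use", at five and nine weeks. The response rate is to be determined in the pilot, and "our initial estimate is at least 70" per cent. Section I.1, in contrast, describes the first survey as a phone survey.

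Two further places bear on the count. One secondary outcome is "Prevalence of symptoms of respiratory infection among all individuals for whom we collect phone numbers". The serology item selects people for blood testing "Among adults who report respiratory symptoms in any of our telephone surveys", and the section on assessing infection by serology illustrates the volume: "if 5% of the 350,000 respondents in the market+ experiment report respiratory symptoms, we will conduct 17,500 such tests".

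**The concern.** Section V.3 speaks of people successfully surveyed, which means completed surveys and not adults approached. The number it gives equals the whole expected adult population of the 700 villages. An incomplete phone response and a complete count cannot both hold for the same wave. No part of the protocol gives a larger frame, replacement sampling or an allowance for non-response that would close the gap.

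This is the enrolment number put to the IRB, and the protocol says that it rests on power calculations. The phone waves also matter more than ordinary follow-up, because symptoms reported by telephone decide who is tested for the primary outcome.

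**Working it through.** **Inputs.** Markets+: 700 (Study Design). Adults per market+: about 500 (Study Design). Phone response: at least 70%, a pre-pilot estimate (Data collection). Illustrative symptom rate: 5% (serology section). The 80% and 90% response rates are assumptions, used to show the range.

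**The plan's own figure.** 700 × 500 × 1.00 = 350,000. It reproduces exactly, but only at 100% response. At 97% the count is 339,500, still 3% short.

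**Completed surveys per follow-up phone wave**, taking the rate over all adults (700 × 500 × r):

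| Response r | Per market+ | All markets+ | Against 350,000 |
|---|---|---|---|
| 70% | 350 | 245,000 | −30% |
| 80% | 400 | 280,000 | −20% |
| 90% | 450 | 315,000 | −10% |

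If the 70% applies only to people with a phone number, and a share c of adults has one, the count is 350,000 × c × 0.70. That is below 245,000 for any c under 1. The protocol does not give c.

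**Frame needed to meet the stated count.** 500 / 0.70 ≈ 715 adults per market+, about 500,000 in total, against the roughly 500 per village expected.

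**All three waves.** The stated total is 3 × 350,000 = 1,050,000.
- In-person baseline, assumed fully completed, plus two phone waves at 70%: 350,000 + 2 × 245,000 = 840,000, which is 20% fewer.
- Three phone waves at 70%, as Section I.1 would imply: 3 × 245,000 = 735,000, which is 30% fewer.

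**The serology example.** With two phone waves at 70% of all adults, the share reached at least once lies between 70% (the same people answer both times) and 100% (since 2 × 0.70 exceeds 1). That is 245,000 to 350,000 people. Independent response would give 1 − 0.30² = 91%, or 318,500. At 5% symptomatic:
- 0.05 × 350,000 = 17,500 tests, the protocol's figure;
- 0.05 × 245,000 = 12,250 tests if only 245,000 are reached.

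Both are before any refusal of blood.

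**Precision, under assumed intracluster correlations** (the protocol gives none). The variance of a cluster mean is proportional to (1 + (m − 1)ρ)/m. Going from m = 500 to m = 350 raises the standard error by:
- ρ = 0.01: √(0.01283 / 0.01198) = 1.035, or about 3.5%;
- ρ = 0.001: √(0.003854 / 0.002998) = 1.13, or about 13%;
- ρ = 0: √(500 / 350) = 1.195, or about 20%.

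**The case against.** The 70% is a stated minimum and provisional, pending the pilot, so a higher rate is not excluded. That is true, but only a rate near 100% matches the stated count, and nothing in the protocol supports one. The village size is also approximate, yet rounding does not explain a gap of up to 30%.

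The serology figure is introduced as an example with a hypothetical 5%, and people missed in one phone wave may be reached in the other. This stands. A reader might infer that the 17,500 tests contradict the response rate. They do not: they are the best case, reached if every adult answers at least one phone wave.

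A reader might also take 245,000 respondents and 12,250 tests as guaranteed minimums. The protocol does not support that. It does not say what the 70% is a percentage of, one symptom outcome is confined to people whose numbers were collected, and some people will decline the blood test.

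Finally, the number of clusters does not change and the protocol plans to monitor response by arm, so the consequence may be modest. This also stands, and it limits the weight of the point.

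**Conclusion.** The inconsistency is real. On the protocol's own figures, 350,000 is the approximate adult population, and it cannot also be the expected number of completed surveys in the follow-up phone waves. If the 70% applies to all adults, the overstatement in each of those waves is 30%; it shrinks as response rises and grows if the 70% is conditional on having a phone number.

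The in-person baseline described under Data collection is not contradicted by the phone response rate, although 350,000 completed surveys there assumes that every adult consents and takes part. Whether the shortfall affects two waves or three depends on reconciling Section I.1 with Data collection.

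A reader might go further and infer that the trial is underpowered. The document does not support this. The serology section says "Power will be similar to our respiratory disease calculation above", but that calculation is not in the text at hand, so it cannot be known whether it already allows for non-response. With 700 clusters unchanged, the loss of precision may be small.

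**What to change.** 1. In Sections IV.8 and V.3, give 350,000 as the adults approached. Separately, give the expected completed surveys per follow-up phone wave as 350,000 times the response rate, about 245,000 at 70% of all adults.
2. State the denominator of the 70% (all adults, households, or people with a phone number), and update the rate and the counts from the pilot.
3. Reconcile Section I.1 with Data collection on whether the first survey is by phone or in person, since this decides how many waves the phone response rate applies to.
4. In the serology section, note that 350,000 respondents and 17,500 tests at 5% are a best case, and that 245,000 reached would give 12,250 before refusal of blood.

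The cost is wording only. No extra enrolment or design change follows; the stated figures become less favourable.
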